### 27c) Select the VA Sensitive Information (VASI) use category

- This study does not collect or use any VASI
- This study uses but does not save, collect, copy, or record VASI
- This study does collect or record VASI

## Section 27.1 VA Sensitive Information (VASI)

### 27.1a) For each type of VASI, indicate all that apply:

Indicate which of the following will be collected/recorded:

- Protected Health Information (PHI)
- Names
- Device identifiers and serial numbers
- E-mail addresses
- Medical record numbers
- URLs (Universal Resource Locator)
- All elements of dates (except year) or any age over 89
- Health plan beneficiary numbers
- IP Addresses (Internet Protocol)
- Telephone numbers
- Account numbers
- Biometric Identifiers including finger and voice print
- Fax numbers
- Certificate or license numbers
- Full face photographic images and comparable images
- All geographic subdivisions smaller than a state
- Vehicle ID and serial numbers including license plate numbers
- Social security numbers or scrambled SSNs (describe below)
- Other unique identifying number, characteristic, or code (describe below)

27.1a1) Describe why SSN are needed for this study

Subject payment and use of clinical record.

27.1a2) Identify the specific other identifier/s that will be used or recorded

Date of birth for non-veteran partners. We must collect this in order to complete the form for opening a collateral medical record for non-veterans, in case doing so is needed to document a safety concern or other non-veteran partner information.

**27.1b) Consent Forms and/or HIPAA Authorization**

Yes  No

**27.1c) Images with personal identifiers are used for this study (x-rays, MRI images with patient names, record numbers, dates, etc.)?**

Yes  No

**27.1d) Photos with faces or audio video recordings are used for this study.**

Yes  No

27.1d1) Identify the device or devices that will be used to take/make the photographs or recordings.

Audacity

27.1d2) Identify where images will be stored (e.g., in the medical record, with study hardcopy records, with study electronic VASI records

The study will collect audio recordings of patient-therapist meetings and assessments. These recordings are considered PHI under HIPAA and VA definition of PHI. These audio recordings will be collected using Audacity. The audio recordings will be saved directly to a secure VA share drive and labelled with anonymous study subject IDs. Only study personnel will have access to the audio recordings. A VA-approved USB microphone that is not capable of storing any data on it will be used to enhance the sound quality. Audio-recordings will be deleted when permitted pursuant to the VA Record Retention Schedule.

**27.1e) Biological specimens with identifiers are used for this study.**

Yes  No

**Section 27.2 Data Collection, Tools, and Resources****27.2a) Will any specially obtained software be used?**

Yes  No

**27.2b) Will any mobile devices (laptop, tablet, portable hard-drive, etc.) be used in support of this study?**

Yes  No

**27.2c) Does the study require use of an electronic data capture system?**

Yes  No

**27.2d) Will any other web-based applications be used (e.g., for recruitment, completing online questionnaires, or processing data)?**

Yes  No

**27.2e) Will coded data that excludes personal identifiers be used? Coded data excludes *all* HIPAA identifiers (per VHA Handbook 1605.1 Appendix B), including dates**

Yes  No

27.2e1) Identify where the code key is stored and in what format (electronic, paper).

Electronically in an Access database on a secure VA research server accessible only on VA-networked password-protected computers.

### Section 27.3 Data Sharing and Transportation

**27.3a) Does this study involve collecting, sharing or transporting any type of data outside of the local VA?**

Yes  No

**27.3b) This study collects VASI outside of VA (i.e., at a non-VA location).**

Yes  No

27.3b1) Describe what is collected outside the VA and how it is secured in transit back to the VA. *Note: An approved Authorization to Transport will be required.*

Clinical contact is provided to Veteran's homes via VA Video Connect, VA's secure clinical video telehealth system, and Webex.

**27.3c) VASI is transported outside of VA for any purpose other than sharing.**

Yes  No

**27.3d) PHI may be disclosed to monitoring/auditing agencies by HIPAA Authorization. *Note: The Research Office must be notified when monitors come to audit***

Yes  No

### 27.3e) Data may be shared with collaborators or others in the conduct of this protocol.

Yes  No

27.3e1) Describe the data to be shared or disclosed, the entities to which the data are to be disclosed, how the data are to be transmitted, and how the transmitted data will be stored, retained, destroyed, and/or further disclosed and to whom. This includes data from individual subjects as well as other data developed during the research such as the analytic data and the aggregate data. For PHI and VASI, indicate the authority/ies permitting the sharing or disclosure of data (HIPAA Authorization, Limited Data Set, Data Use Agreement, VA Form 10-5345-Request for and Authorization to Release Health Information., etc.).

In general, it is unlikely that de-identified study data will be sent to collaborators. On the rare occasion that de-identified data is shared with collaborators, an Excel database would be stripped of identifiers other than the subject ID. The data sets will not contain any of the 18 HIPAA personal identifiers, and collaborators will not have access to linkage information. This Excel database would include baseline and outcome self-report measures data and would be shared for the purpose of descriptive and/or differential analysis. The files would be sent via encrypted email and would be password protected. The passwords would then be sent in a separate email to ensure security.

## Section 27.4 Research Record Storage and Retention

For each type of record, indicate whether it is collected for this study

### 27.4a) Hardcopy records/data (includes paper, pictures, film, etc.)

Yes  No

27.4a1) Identify precisely where hardcopy data will be stored to include physical site, building, and room number, etc. For each location identify whether VASI or non-sensitive information is stored at that location. For VASI, identify how the data is secured.

Physical VASI records will be kept in locked cabinets in a locked office (room 418) in Building 13 at the Veterans Medical Research Foundation. Data will be retained in accordance with VA record control schedule RCS 10-1.

27.4a2) Are all of the above locations at VA?

Yes  No

### 27.4b) Electronic study records (includes computer files, removable disk files, digital files, etc.).

Yes  No

27.4b1) Identify precisely where **non-sensitive** electronic records/data will be stored to include the full map drive, network location/server name, etc., and a brief description of what data/information is stored at each location.

S Drive; PI folder: [name]

Assessment measures, recruitment materials, consent documents, etc.

27.4b2) Identify precisely where **VASI** electronic records/data will be stored to include the full map drive, network location/server name, etc., and a brief description of what data/information is stored at each location.

If no VASI is collected or recorded for this study, simply indicate that the “Study does not collect or record VASI”.

S Drive; PI folder: [name]

Names, phone numbers, last 4, and addresses are stored in an encrypted file at the location listed above.

27.4b3) Are any of the locations described in 27.4b outside of the VA Secure Network? *Note: this includes storage on a computer local hard drive.*

Yes  No

**27.4c) Record Retention - VHA requires compliance with Records Control Schedule (RCS-10) for retention of electronic and hard copy records. Following study closure, these temporary records must be retained for six years and then destroyed. Longer retention may be permitted if required by other Federal regulations or requirements. Will RCS-10 requirements be followed (i.e., 6-year retention)?**

I will adhere to VHA Records Control Schedule-10 requirements  
 I request an exception to RCS-10 requirements

## Section 27.5 Additional Privacy or Information Security Details

Provide any other privacy or information security details here.

NA

## Section 27.6 Attestations

**In the event of real or suspected breach of security, the Information Security Officer, Privacy Officer, VA Police (if appropriate), and the individual's supervisor will be notified within one hour of learning of the event.**

Agree  Disagree

**Study staff will be up to date on any required VHA Privacy Policy and Information Security training or they will not be allowed access to VA Sensitive Information.**

Agree  Disagree

**Access to research sensitive information, if any, will be removed when study personnel are no longer part of the research team.**

Agree  Disagree

**At least one copy of all study records (whether sensitive or non-sensitive) will be retained under VA control and only destroyed in compliance with the approved Records Control Schedule**

Agree  Disagree

**The VA retains ownership of the research data. Should the investigator leave the VA, custody of the research records will be assigned to another investigator and the Research Service notified in writing, or custody of the research records will be transferred to the Research Service.**

Agree  Disagree

## Section 28 - Protocol Association to New or Existing Project

**28) Is this a new R&D Project? Before you go on to complete the *Initial Review Submission Form* (which is used for attachments), please address the association of this Protocol to an R&D Committee Project. This Protocol may represent a new R&D Project, or it may be an additional Protocol under an existing R&D Project (such as when a single grant supports multiple Protocols). Will this Protocol be submitted to the R&D Committee as a new Project?**

Yes  No

**The Protocol Application is now complete for a Protocol that will also be a new R&D Committee Project.**

**Next you will go on to the Initial Review Submission Form which is used to package up the Protocol Application and any needed attachments and submit them to the IRB.**

**Click on *Save and Continue***

Brief Cognitive Behavioral Conjoint Therapy for PTSD With Adjunctive Intranasal Oxytocin (CBCT+OT)

NCT05207436

2/15/23

Data Analytic Plan

Primary analyses with the intent-to-treat sample evaluated change in PTSD symptoms and relationship satisfaction using weekly session, baseline, and post-treatment data analyzed with multilevel linear growth models in the *R* package lme4 and a Kenward-Roger small samples correction. To account for dyadic interdependence, time was nested within individuals and individuals were nested within couples. Analyses included two-intercept models, which produce separate slope and intercept estimates for PTSD+ veterans and non-PTSD+ partners, and a separate interaction model to test for differences between slope and intercept estimates for veterans and partners. PTSD data was composed of veteran PCL-5 and partner/collateral PCL-5 scores. Relationship satisfaction data were CSI-4 scores for both partners; at baseline and post-treatment, the four items comprising the CSI-4 were extracted from the CSI-32 to be included in growth curve analyses.

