**Section 6 - Specific Aims**

**6) Provide a statement of specific aims and hypotheses that serve as the basis for this protocol. Emphasize those aspects that justify the use of human subjects.**

The goal of this proposal is to examine the initial clinical feasibility of B-CBCT augmented with intranasal oxytocin (B-CBCT + OT) for improving relationship satisfaction in an open trial among twenty dyads composed of Veterans with PTSD and their intimate partners. We also plan to explore secondary outcomes such as PTSD symptoms, other aspects of social functioning, and quality of life.

In addition to establishing feasibility of methods (i.e., recruitment and retention of dyads and acceptability to participants), specific hypotheses for this project are as follows:

- Primary Hypothesis: There will be improvements in each partner's self-reported relationship satisfaction measured by the Couples Satisfaction Index following completion of B-CBCT + OT.
- Secondary Hypotheses: Following the completion of B-CBCT + OT, Veterans will report improvements in PTSD symptoms measured by the PTSD Checklist for DSM-5, psychosocial functioning measured with the Brief Inventory of Psychosocial Functioning, and quality of life measured with the World Health Organization Quality of Life – BREF.

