To this end, [name] (PI) recently completed a study of an 8-session version of CBCT (B-CBCT) delivered either in-office or via telehealth to home compared to a family education control condition, designed to improve access to and retention in care. She and her team similarly found robust reductions in PTSD symptoms in B-CBCT (B-CBCT within-group  $d's = 1.05-1.12$ , between-group  $d's = 0.59-0.76$ ) but only a small effect on both partners' relationship satisfaction that was on par with the family education condition (B-CBCT within-group  $d = 0.38$ ; b between-group  $d's = 0.04-0.12$ ).

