### STUDY DESIGN OVERVIEW:

This pilot study will enroll up to 20 couples (40 individuals) in B-CBCT + OT over this 12-month project. Participants will be recruited from the San Diego VA Healthcare System. Couples will participate in 8 sessions of B-CBCT augmented with 40 IU of intranasal oxytocin administered 30 min before each session. At baseline and post-treatment, dyads will be asked to complete brief assessments of the outcomes described above. After treatment, they will also provide feedback about factors associated with feasibility of methods and treatment engagement. Quantitative and qualitative data will be used to assess the feasibility and acceptability of the intervention and will be utilized in preparing a proposal for an RCT. We will compare within-group effect sizes on PTSD and relationship satisfaction to effects observed within the historical controls from [name] RCT of B-CBCT.

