## DATA COLLECTION:

Responses to measures at all assessment time points are collected with each partner individually with the other partner leaving the room to avoid coercion or fear of reprisal if one partner were to disclose disqualifying information such as domestic violence. Participants will complete the following measures prior to study enrollment to determine if inclusion/exclusion criteria are met:

- *PTSD Checklist for DSM-5* (PCL-5; Weathers et al., 2013) – 20-item self-report measure for the past month that assesses symptoms of PTSD based on the DSM-5; scores at or above 33 indicate probable PTSD. Couples will be included if the veteran partner scores at or above 33 on this measure.
- *Columbia-Suicide Severity Rating Scale* (C-SSRS; Posner et al., 2011) – 8-item self-report measure of suicidal ideation, plan, and intent. Individuals who endorse acute suicidality will be excluded from the study.
- *IPV Assessment-Extended* (IPV-5) – assesses behaviors that individuals engage in during conflict with their partner as well as past and current fear and intimidation in the relationship. Couples with individuals who endorse any severe physical assault behaviors in the past year will be excluded from the study.
- *Alcohol Use Disorders Identification Test* (AUDIT; Bohn et al., 1995) – measures problematic substance use. Individuals endorsing symptoms of an active substance use disorder will be excluded.

Additional measures administered at baseline assessment only include:

- *Traumatic Life Events Checklist* (TLEC; Blake et al., 1995) – a 17-item self-report scale that assesses for a lifetime history of exposure to traumatic events (veteran only)
- *Demographic information and past experiences receiving mental health treatment* (both partners)
- *Coronavirus Stressor Survey* – assesses stress related to COVID19 (both partners)

The primary (relationship satisfaction) and secondary (PTSD symptoms, quality of life) outcomes will be assessed with both partners at baseline, post-intervention, and three months post-intervention using the following quantitative measures:

- *Couples Satisfaction Inventory-32* (CSI-32; Funk & Rogge, 2007) – a well-validated measure of relationship satisfaction
- *Changes in Sexual Functioning Questionnaire Male Clinical* (CSFQ-M; Keller et al., 2006) – the male version of a 14-item measure that provides a brief measure of sexual functioning with good construct validity and internal reliability

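### The SAP puts PTSD symptoms and relationship satisfaction together under its primary label without ranking them, although the protocol makes each partner's satisfaction the only primary outcome

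*SAP*

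**What the plan says.** The protocol ranks its outcomes twice. Section 6 has one primary hypothesis: improvement in each partner's "self-reported relationship satisfaction measured by the Couples Satisfaction Index following completion of B-CBCT + OT". PTSD comes below it: "We also plan to explore secondary outcomes such as PTSD symptoms, other aspects of social functioning, and quality of life". The secondary hypotheses concern veterans only: "Veterans will report improvements in PTSD symptoms measured by the PTSD Checklist for DSM-5, psychosocial functioning measured with the Brief Inventory of Psychosocial Functioning". The WHOQOL-BREF is the third measure named there. Section 9, Data Collection, repeats the order: "The primary (relationship satisfaction) and secondary (PTSD symptoms, quality of life) outcomes will be assessed with both partners at baseline". That section lists the CSI-32 for baseline, post-intervention and three months, and the CSI-4 before each session.

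The SAP is one paragraph. It says "Primary analyses with the intent-to-treat sample evaluated change in PTSD symptoms and relationship satisfaction" and gives no order. On content it adds "PTSD data was composed of veteran PCL-5 and partner/collateral PCL-5 scores", with CSI-4 for both partners; at baseline and post-treatment the CSI-4 items are taken from the CSI-32. Its two-intercept models give separate slopes for veterans and partners. It names neither the B-IPF nor the WHOQOL-BREF, and it has no section on secondary analyses.

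**The concern.** The study adds oxytocin because B-CBCT already works on PTSD but does little for satisfaction. Protocol Section 7 reports that B-CBCT alone had within-group d of 1.05-1.12 on PTSD. On satisfaction it had d = 0.38, an effect on both partners' "relationship satisfaction that was on par with the family education condition". A PTSD improvement is therefore expected even if oxytocin adds nothing.

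If that improvement carries the primary label, the trial could be reported as positive on a primary analysis while the question in Section 6 is unanswered or null. This matters beyond the pilot, because Section 9 says the data will be used in preparing an RCT proposal. Separately, two of the three secondary hypotheses have no described analysis.

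**Working it through.** **Side by side.** The SAP's primary label covers four slopes (two outcomes by two roles):

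| Slope in the SAP | Status in Protocol Section 6 |
|---|---|
| CSI-4, veteran | primary |
| CSI-4, partner | primary |
| PCL-5, veteran | secondary |
| PCL-5, collateral | in no hypothesis (listed as a measure in Section 9) |

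Two of the four belong to the primary hypothesis. Conversely, B-IPF and WHOQOL-BREF are in Section 6 and absent from the SAP. The protocol does not fill that gap: its only analytic statement about outcomes is the historical-control comparison of effect sizes, which covers PTSD and satisfaction.

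**Illustration.** The documents give no alpha, power or correlation, so there is no figure to reproduce.

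*Inputs from the protocol:* d = 0.38 and d = 1.05 (Section 7, B-CBCT alone); up to 20 couples; eight weekly sessions; baseline and post-treatment 20 to 28 weeks apart (Section 9).

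*Assumptions:* 20 complete couples, d in units of the baseline SD, two-sided 5% t test with 19 df, pre-post correlation r = 0.5. Let f be the share of change variance that is true between-person slope variation, from 0 to 0.75.

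*Formula:* with time scaled 0 to 1 from baseline to post, SD of a slope = sqrt(2f(1-r) + (1-f)(1-r)/Sxx), where Sxx is the sum of squared deviations of the ten time points.

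- Sessions early or late in 28 weeks: Sxx = 0.738. At f = 0, SD = sqrt(0.5/0.738) = 0.823, and satisfaction power per partner is 0.50.
- Sessions in the middle of 28 weeks: Sxx = 0.554. At f = 0.75, SD = sqrt(0.75 + 0.125/0.554) = 0.988, and power is 0.37.
- The 20-week interval falls between these. Power per partner is thus about 37-50%.
- Ten equally spaced points would give Sxx = 1.019 and power of 41-63%, but weekly sessions inside 20 to 28 weeks are not equally spaced with the two assessments.
- PTSD power at r = 0.5 is at least 99%.

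*Joint event (PTSD significant, neither partner's satisfaction significant).* With independent changes this is close to (1 - 0.50)² = 0.25 at one end and (1 - 0.372)² = 0.39 at the other. Simulation with correlations of 0 to 0.6 between partners' changes and 0 to 0.3 between PTSD and satisfaction changes gives about 24-48%.

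**Precision of a simple change estimate.** Half-width of the 95% CI = t × sqrt(2(1-r)/n), in baseline SDs:

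| n | t | r = 0.3 | r = 0.5 | r = 0.7 |
|---|---|---|---|---|
| 20 | 2.093 | 0.55 | 0.47 | 0.36 |
| 14 | 2.160 | 0.68 | 0.58 | 0.45 |

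With 14 completers, the lowest PTSD power in a paired pre-post test (r = 0.3) is 0.87, against 0.96 with 20.

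**The case against.** The SAP speaks of primary analyses, not primary outcomes, and may only mean the main analyses: PCL-5 and CSI-4 are the two measures taken before every session. It fits separate models and gives role-specific slopes. The protocol also pairs the two outcomes elsewhere without ranking them. Section 9 does so for the historical comparison ("We will compare within-group effect sizes on PTSD and relationship satisfaction to effects observed within the historical controls"), and Section 12.1 does so in what participants are told about the purpose. This is also a single-arm feasibility pilot.

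Much of this limits the point. A reader might infer that the sponsor switched the primary outcome, that a PTSD result alone is defined as success, or that a stated error rate is breached. The documents support none of these. The SAP sets no composite, success rule or alpha, and it still tests each partner's satisfaction. Its past tense does not show that results drove the label.

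What remains is that the SAP does not say it means main analyses, so a reader cannot tell which result decides the Section 6 hypothesis. Unranked pairings elsewhere do not undo two explicit rankings. It is also fair that the joint-event probability is the same before and after relabelling, and that it rests on a significance rule the documents never state. It shows only that the two outcomes could plausibly diverge.

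**Conclusion.** The point holds as a conflict of labels, with a lesser omission. The protocol ranks satisfaction above PTSD symptoms in two places, and the SAP places both under one primary label, unranked and without a reason. That finding rests on the text alone.

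The illustrative size is 37-50% power per partner for satisfaction and about 24-48% for the divergent result. Both depend on B-CBCT-alone effects, r = 0.5, a two-sided 5% test and 20 complete couples. Fewer completers lower power and widen intervals. Correcting the label would not let a single-arm study isolate the effect of oxytocin; it would tie the reported primary result to the protocol's own question. The missing B-IPF and WHOQOL-BREF analyses would, alone, be a minor gap. The correction should be made, but it does not invalidate the planned models.

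**What to change.** In the SAP:

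1. Name each partner's relationship satisfaction as the only primary outcome. Keep the existing CSI-4 growth models as its analysis and report the veteran and partner slopes separately, each with a 95% CI. Report CSI-32 baseline-to-post change alongside, because the protocol lists the CSI-32 for those waves.
2. Label the veteran PCL-5 model secondary and the collateral PCL-5 model secondary or exploratory. State that PTSD results do not decide the primary hypothesis.
3. As a lesser point, add baseline-to-post change with a 95% CI in the intent-to-treat sample for veterans' B-IPF and WHOQOL-BREF, and say how missing post-treatment values are handled. Use the same B-IPF recall version at both waves, since Section 9 describes a two-week version used during treatment. Report all four WHOQOL-BREF domains, so that none is chosen afterwards.
4. Date the change and say whether results were already known, because the SAP is in the past tense.

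The cost is a few sentences and some simple estimates on data already collected. The downside is a headline that may be less favourable. With independent changes, both satisfaction slopes would be significant in only about 0.372² = 14% to 0.50² = 25% of trials under the assumptions above; correlation between partners raises this. If results were already known, the change restores the protocol's ranking in the report but not prespecification.
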